The moderation/mediation analyses described above are exploratory in nature. As a result we will not implement a multiplicity adjustment for these analyses. Study researchers will ensure that publications report all the analysis results and specify the total number of exploratory analyses that were conducted.

Sub-Study:

We will pair sleep data with the demographic and descriptive information as well as the pain outcomes that are collected as part of the main study. All data will be de-identified and linked only by a participant ID code and all data sharing will be done in accordance with the collaborating institutional human participants' committees.

For aim 1 of this supplemental study, the primary outcome measures are (1) self-reported sleep quality (subjective sleep assessment on the continuum from “good” to “poor” sleep), and (2) actigraphic sleep duration (the total amount of sleep per 24 hours measured objectively with wrist actigraphy). Secondary outcomes include self-reported and actigraphy-based sleep timing and continuity.

For the statistical analyses in support of aim 1, we will compare sleep quality and duration in self-hypnosis and mindfulness meditation treatment groups as measured by self-report and through wrist actigraphy from pre-treatment to immediate post-treatment, and at 3-month follow-up, relative to sleep quality and duration at the same time points in the education control group. *We hypothesize that participants in the two treatment groups will show improvements in self-reported sleep quality and in actigraphic sleep duration both immediately post-treatment and at 3-month follow-up, relative to the control group.* We will test this hypothesis, for each of the two primary outcome measures, by means of mixed-effects analysis of variance (ANOVA), where a random effect will be placed on the intercept, and the hypothesis tested with planned contrasts between conditions, at each time point, embedded in the mixed-effects ANOVA framework.⁹² Secondary analyses will use additional key demographic variables (age, sex/gender, race/ethnicity, medications) as covariates.

For aim 2 of this supplemental study, the primary outcome measures will be paired with the primary pain outcome from the parent grant as measured with a 0–10 numeric pain intensity scale.⁴¹

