We base our power calculation on a previous study that is informative of the statistical power found in sleep duration data from wrist actigraphy as collected in naturalistic repeated-measures settings. In this previous study, 24 regional airline pilots participated in a two-day flight simulator study.¹⁰⁷ In the day before the study, they flew into the airport where the flight simulator center was located, and that night they planned their sleep naturalistically. As the pilots discovered that the workload during the study was high, they extended their sleep in the night between the two study days in order to recuperate. As measured by wrist actigraphy (same type as will be used in the supplement), the sleep duration in the night prior to the second study day was significantly greater than the sleep duration in the night prior to the first study day, by a difference of 1.35 hours ($t_{23}=3.97$, $P<0.001$). The correlation of sleep duration between nights was $\rho=0.122$. Relevant for our power calculation is also the systematic between-subjects standard deviation, which was $SD=26.3$ minutes.

In aim 1 of the supplemental study, we will use wrist actigraphy to compare sleep pre-treatment to immediately post-treatment (8 weeks) and to 3-month follow-up, relative to sleep at the same time points in the control group. Thus, we will make two repeated-measures comparisons: pre-treatment to post-treatment in the intervention group relative to the control group, and pre-treatment to 3-month follow-up in the intervention group relative to the control group. Because each of these two comparisons defines an interaction effect, which is inherently low on statistical power, we set the a-priori type I error threshold to $\alpha=0.1$.¹⁰⁸ However, because we will do two comparisons using the same pre-treatment data, we must also control for multiple comparisons. Therefore, after applying Bonferroni correction, we end up with a type I error threshold of $\alpha=0.05$.

To make use of the statistical power conferred by systematic between-subjects variability,¹⁰² we will employ mixed-effects ANOVA to implement the test (which then again takes the form of an interaction effect).

For power calculation purposes this is relevant in that the standard deviation of interest is therefore the systematic between-subjects standard deviation provided above (which, in a comparison between independent samples, serves as the estimated pooled standard deviation).

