Also, as we expect that treatment will improve sleep and we will only consider the effect beneficial if it involves extension of sleep duration, one-sided testing will be used. We will consider a mean increase in sleep duration of $M=15$ minutes or more to be clinically relevant.¹⁰⁹ Thus, we seek to demonstrate an effect size of Cohen's $d=M/SD=15/26.3=0.57$. To achieve 80% statistical power at a type I error threshold of $\alpha=0.05$, we will need to study 39 participants per group (nQuery 7.0, Elashoff, 2007). Thus, we will need to study 39 participants in each of the two treatment groups and 39 participants in the control group. As such, our target sample size for the supplemental study is $N=117$.

For aim 2 of the supplemental study, with 39 subjects in each treatment group we will have the ability to investigate the relationship between actigraphically measured sleep duration and pain outcomes from the parent project. For each of the two intervention groups, we will first use a regression model on subjective pain with sleep duration as the covariate of interest, and our objective will be to test the regression coefficient for this covariate against zero (two-tailed). With 39 subjects, we will have 80% statistical power, at a type I error threshold of $\alpha=0.05$, to detect a relationship between sleep duration and subjective pain if this relationship explains at least 17.5% of the variance (nQuery 7.0, Elashoff, 2007).

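### The sleep sub-study's Bonferroni step counts only two time points, while the plan implies up to eight primary contrasts, so its stated control of multiple comparisons at 0.10 is not delivered

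*Combined protocol and SAP*

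**What the plan says.** Two sections of the combined protocol and SAP bear on this, both under their sub-study headings.

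- **D6z, Power Calculations (Sub-Study).** For Aim 1, "we will make two repeated-measures comparisons": pre-treatment to post-treatment, and pre-treatment to 3-month follow-up, each in the intervention group (singular) relative to control. The section starts from a type I error of 0.10. It then says that "because we will do two comparisons using the same pre-treatment data, we must also control for multiple comparisons", and Bonferroni brings the level to 0.05. One-sided testing is adopted on the ground that only longer sleep would count as benefit. With a 15-minute difference and an SD of 26.3 minutes, "we will need to study 39 participants in each of the two treatment groups and 39 participants in the control group", 117 in total.
- **D6x, Statistical Analyses, Sub-Study.** Aim 1 has two primary outcomes, self-reported sleep quality and actigraphic sleep duration. The hypothesis concerns both the self-hypnosis (HYP) and mindfulness (MM) groups relative to education (ED), at post-treatment and at 3 months. It is tested "for each of the two primary outcome measures" in a mixed-effects ANOVA, by "planned contrasts between conditions, at each time point".

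No other multiplicity rule covers these contrasts. The Tukey method in D6x belongs to the main study. The statement in the sub-study text that no correction is planned concerns exploratory mediator analyses.

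**The concern.** The power section accepts that multiplicity must be controlled and names the level, but its divisor covers only one of the three ways in which the primary tests multiply. Two treatments and two primary outcomes are left out of the count. The starting level has already been relaxed to 0.10, so halving it returns each test to 0.05.

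What is at stake is how a positive sleep finding may be described. A report could call one significant contrast Bonferroni-controlled although the chance of at least one false positive, across the contrasts the plan treats as primary, is above the stated level. The main trial's pain outcome is not affected.

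**Working it through.** **1. The plan's own figures.** From D6z: 0.10/2 = 0.05; d = 15/26.3 = 0.570. For a one-sided two-sample comparison at 0.05 with 39 per group, the noncentrality is 0.570 × √(39/2) = 2.52. Power is Φ(2.52 − 1.645) = 0.81 by the normal approximation and 0.803 by the noncentral t. Total 3 × 39 = 117. All of this reproduces. A two-sided test at 0.05 would need 49 per group, so 39 does rest on one-sided testing.

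**2. The count.** Treatments against ED: 2 (the hypothesis in D6x; per-arm sizing in D6z). Time points: 2. Primary outcomes: 2 (D6x).

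- Duration only, each arm separately: 2 × 2 = 4.
- Both outcomes, each arm separately: 2 × 2 × 2 = 8.
- Both outcomes, arms pooled: 2 × 2 = 4.
- Duration only, arms pooled: 2, the only one of these four readings that matches the divisor.

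**3. Familywise error with each test at 0.05.** The upper bound is k × 0.05. Under independence the error is 1 − 0.95^k. The correlated figures are simulated as the probability that the largest of k correlated standard normal statistics exceeds 1.645.

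The correlations are assumptions, not figures from the documents: 0.5 between arms (what a shared control gives with equal groups), 0.5-0.7 between time points, 0-0.5 between outcomes.

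| Family | k | Bound | Independent | Assumed correlations |
|---|---|---|---|---|
| Duration, arms pooled | 2 | 10% | 9.8% | 8-9% |
| Duration, two arms | 4 | 20% | 18.5% | 14-15% |
| Both outcomes, arms pooled | 4 | 20% | 18.5% | 14-17% |
| Both outcomes, two arms, all one-sided | 8 | 40% | 33.7% | 23-28% |

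If the four sleep-quality tests are two-sided at 0.05, the last figure becomes about 25-29%.

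**4. Power once the family is counted.** With 39 per group and d = 0.57 (noncentral t):

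- Four contrasts: 0.10/4 = 0.025, first-step power 70%.
- Eight contrasts: 0.10/8 = 0.0125, first-step power 59%.

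These are floors for any one contrast, because Holm's later steps use larger levels. Simulating Holm at an overall 0.10 under the same correlations (normal approximation, all tests one-sided, every contrast at d = 0.57) gives average per-contrast power of about 81-82% for four contrasts and 75-76% for eight.

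**The case against.** The best defence is that the family is a matter of choice. The power section says it focuses on actigraphy, so 0.10/2 was never presented as covering sleep quality. Separate claims for each treatment and each outcome can be defended in a multi-arm trial, and within one treatment and one outcome the plan's 0.10 is met. The text also speaks of a single intervention group and does not list the contrasts. If the arms were pooled and duration alone were primary, the divisor of 2 would be right.

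Part of this stands. Eight is inferred, not stated, and the fair criticism is that the family is undefined. But sizing 39 in each treatment group points away from pooling, and D6x gives sleep quality equal primary status. The plan also does not say that error is controlled separately by treatment or outcome. Leaving either treatment or outcome out of the count still gives four contrasts and an error above 0.10.

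Three stronger readings are tempting, and the documents do not support them:

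- **Eight one-sided tests.** One-sidedness is justified only by longer sleep duration. No sidedness is given for the sleep-quality contrasts.
- **Every contrast must succeed, so 80% power is badly overstated.** The plan states no such rule, and applying Bonferroni points the other way.
- **Correction cuts power from 80% to 70% or 59%.** Those are first-step floors, not the power that Holm delivers overall.

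Enrolment has also risen to 195. With the 25-30% drop-out in D5, that is 195 × 0.70 to 195 × 0.75, or about 137-146 completers and roughly 45-48 per group. First-step power would then be about 76-79% (four) or 67-70% (eight). This assumes full enrolment. It is optimistic for actigraphy, because a completer needs only one post-randomization assessment (D5) and 10% of devices are expected not to be returned (D6s).

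**Conclusion.** The concern holds as a problem of family definition, not of arithmetic. The plan commits to controlling multiple comparisons and counts two, while its own analysis text and sizing imply up to eight. Only pooled arms with duration alone would keep the error within 0.10, and the documents point away from that. The exact percentages depend on the assumed correlations, but every other reading considered here exceeds 0.10 throughout the assumed range. The Holm averages further assume that all effects equal 0.57, and the plan gives no effect size for sleep quality. This is worth correcting, but it is confined to an optional sub-study.

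**What to change.** In D6x (Sub-Study), list the primary contrasts: which arms are compared with ED, at which time points, on which outcomes, and whether each test is one- or two-sided. Then choose one family and apply Holm at the plan's overall 0.10:

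- all eight contrasts; or
- the four actigraphic-duration contrasts, with duration named as the single primary outcome and sleep quality made secondary.

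In D6z, replace the two-comparison count with the chosen family. Restate power at 39 per group as a guaranteed first-step figure (70% for four, 59% for eight), alongside the average under Holm (about 81-82% or 75-76%) with its assumptions. For the eight-contrast option, an effect size for sleep quality must be stated first.

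The cost is SAP wording and a less favourable guaranteed power figure. No patients, visits or data are added. The choice should be recorded before sleep outcomes are examined by arm.

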Participants will be randomly assigned to 8 group sessions of (1) self-hypnosis (HYP), (2) mindfulness meditation (MM), or (3) an education control condition (ED). Treatment groups will meet once per week over an 8 week period. Each session will last for duration of about 90 minutes. Primary (characteristic pain intensity) and secondary outcomes will be assessed at pre-treatment, three times during treatment, post-treatment, and at 3- and 6-month follow-up. The total time involved in the study is approximately 20-23 hours over a 9-month period.

Once participants complete their involvement in the primary study (i.e., after they have received one of the treatments and completed their last follow-up assessment), they may be invited to attend either (or ultimately both, if they wish) of the other two group treatments. This is called the “open label” phase of the study.

Participants who attend treatment for the first time in cohort 10 and all subsequent cohorts will not be offered the open label phase given study researchers intend to stop running treatment groups by the time these participants will complete the main phase of the study. Instead, these participants will be offered the treatment materials for the treatment of their choice. The treatment materials (workbook and audio recordings) will be mailed via USPS.

Participants who were randomized in cohorts 1-9 and are eligible to participate in the open label phase for cohorts 11 or 12 will be offered the option of either receiving treatment materials in the mail for the treatment of their choice or enrolling in the open label phase depending on space availability.

Sub-Study:

All participants enrolled in the sleep sub-study will be asked to wear a wrist actigraph (Actiwatch 2, Philips Respironics, Bend, OR) for up to 7 consecutive days, up to 24 hours/day to collect objective sleep data at 3 time points: before treatment begins, immediately following the end of treatment, and 3 months following the end of treatment. During each one-week assessment period they will also be asked to complete a brief questionnaire each morning and evening, and fill out a sleep log that includes estimates of time to bed, time to sleep, time awake and out of bed, sleep quality, and daytime napping.

Sample Size and Population

Main Study:

We plan to enroll up to ~~343~~ 355** Veterans with moderate to severe chronic pain to achieve a sample size of 240 completers, with 80 completers in each of the treatment groups.

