Enrolled participants who complete the required baseline components (cognitive assessment, hypnotic and relaxation exercise, baseline data and demographic form, and pre-treatment assessment period) will be randomized in stratified blocks to ensure that participants with each sex/gender and pain type (neuropathic, non-neuropathic, mixed or undetermined) have an equal chance of being randomized to one of the 3 conditions. Stratifying in this manner will ensure the groups are balanced to reduce variation in outcome that is associated with each stratification variable.

Sub-Study:

Recruitment will follow the protocol of the main study. We propose to recruit up to ~~135~~ 180* 195** of the ~~343~~ 355** parent grant participants in order to ensure complete data from 117 participants, assuming a 15% drop-out rate. Based on our experience, we anticipate that at least 75% of the parent sample will elect to join the sleep study.

*Due to a higher attrition rate than anticipated, we have increased the enrollment number from 135 to 180 to ensure the 117 completers needed. A 13% attrition rate was determined based on the main study. The actual attrition rate for the sleep study is 27%.

** Enrollment number increased to allow for the recruitment of a full cohort in the final cohort of the study.

A. SPECIFIC AIMS

A1. Problem Statement

Main Study:

As many as 50% of male and 75% of female Veterans presenting to Primary Care report chronic pain¹⁻⁴, and reporting rates are even higher in specialty clinics.⁵⁻⁷ Among Veterans returning from Iraq and Afghanistan, 82% report chronic pain,⁸ and the prevalence of painful musculoskeletal, joint, and back problems tends to increase in the years following deployment.⁹ Prevalent co-morbidities among Veterans, such as substance use disorders, sleep dysregulation, mood disorders, and Post Traumatic Stress Disorder (PTSD) can amplify the experience of pain and complicate treatment.¹⁰⁻¹² In Veterans, the presence of co-morbid pain and anxiety is associated with increased service utilization,¹³ while co-morbid pain and substance use increases the risk of medication misuse.¹⁴ Pain is also associated with greater depression and anxiety,¹⁵ sleep dysregulation^{12, 16}, decreased quality of life,¹⁷ and lower self-reported health.¹⁸

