If someone is enrolled and not a completer, they would be defined as either 1.) Enrolled, did not select treatment or 2.) Enrolled, selected treatment, did not participate in the post-treatment assessment.

Sub-Study:

We propose to enroll up to up to ~~135~~ ~~180~~ 195 participants in the sub-study to ensure complete data from 117 randomized participants, assuming a 25 - 30% drop-out rate. We will monitor the dropout rate on an ongoing basis, and modify the number of participants recruited as needed to ensure a final sample of N = 117 sub-study completers.

A completer is someone who is enrolled, randomized and participated in at least one data assessment point following randomization.

If someone is enrolled and not a completer, they would be defined as either 1.) Enrolled, not randomized or 2.) Enrolled, randomized, did not provide any data after randomization

Eligibility Criteria

Inclusion criteria:

- (1) Veteran status (defined as prior service in the US Armed Forces and eligible to receive health care services through Veterans Health Affairs);*
- (2) 18 years of age or older; *
- (3) Self-reported presence of chronic pain;**
- (4) Average pain intensity rating of ≥ 3 on a 0-10 Numerical Rating Scale (NRS) of pain intensity in the last week; **
- (5) Worst pain intensity rating of ≥ 5 on a 0-10 Numerical Rating Scale (NRS) of pain intensity in the last week;**
- (6) Duration of chronic pain 3 months or more; **
- (7) Experiences pain at least 75% of the time in the past 3 months; Those who have a hard time answering this question will be asked the following question: "Which statement best describes your pain?"
 - (a) Pain all the time, but the pain intensity varies;
 - (b) Pain most of the time with only occasional periods of being pain-free;
 - (c) Pain that comes and goes;
 - (d) Occasional pain;

Participants must report experiencing pain that matches one of the first two options; **
(8) Able to read, speak, and understand English. **

Exclusion criteria:

- (1) severe cognitive impairment defined as two or more errors on the Six-Item Screener;⁵¹ **
- (2) Current or history of diagnosis of primary psychotic or major thought disorder as listed in participant's medical record or self-reported within the past five years;*
- (3) Hospitalization for psychiatric reasons other than suicidal ideation, homicidal ideation, and/or PTSD self-reported or noted in chart (within the past 5 years);*

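### The sleep sub-study's 39 per group leaves out night-to-night variation; its own pilot figures give about 54% power at best for the planned contrast, not 80%

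*Combined protocol and SAP*

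**What the plan says.** The Power Calculations (Sub-Study) part of D6z takes its variances from a two-night study of 24 airline pilots. Sleep on the second night was "significantly greater than the sleep duration in the night prior to the first study day, by a difference of 1.35 hours", with t on 23 degrees of freedom of 3.97, a between-night correlation of 0.122 and a systematic between-subjects SD of 26.3 min.

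The comparisons to be powered are pre-treatment to post-treatment and pre-treatment to 3 months, intervention against control. The section recognises what this means: "Because each of these two comparisons defines an interaction effect, which is inherently low on statistical power". It then argues that, because a mixed-effects ANOVA will be used, "the standard deviation of interest is therefore the systematic between-subjects standard deviation provided above", and treats that SD as the pooled SD of two independent samples. With a relevant difference of 15 min, a one-sided test and alpha 0.05, it concludes that "we will need to study 39 participants per group", or 117 in three arms.

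The sub-study part of D6x (Statistical Analyses) describes the model as one "where a random effect will be placed on the intercept, and the hypothesis tested with planned contrasts between conditions, at each time point". The Précis says the actigraph is worn "for up to 7 consecutive days, up to 24 hours/day to collect objective sleep data at 3 time points". It also reports that "The actual attrition rate for the sleep study is 27" percent, and D5 plans to enrol up to "195 participants in the sub-study to ensure complete data from 117 randomized participants".

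**The concern.** A random intercept removes stable differences between people from a within-person comparison. It does not remove the variation from night to night within a person. The calculation does the reverse: it keeps the between-person component and drops the within-person one.

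Neither description of the test leaves 26.3 min as the error SD. In the change contrast of D6z the intercept cancels and only within-person error remains. In a contrast between arms at one time point, as D6x can be read, the intercept stays and within-person error is added to it.

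Actigraphic sleep duration is one of two primary outcomes of sub-study Aim 1, and enrolment was first raised, from 135 to 180, to secure the 117 completers that this calculation asks for. If power is well below 80%, a null result read against the stated figure could be taken as evidence against a 15-min benefit that the design was unlikely to detect.

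**Working it through.** **Inputs.** From D6z: difference 1.35 h = 81 min; t = 3.97; n = 24; correlation 0.122; SD 26.3 min; effect 15 min; one-sided alpha 0.05; 39 per group. From the Précis: up to seven nights per period, 195 enrolled, 27% attrition. Power is from the noncentral t distribution.

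**The plan's figure.** With SD 26.3 min and 39 per group, power is 80.3%, and 39 is the smallest group size that reaches 80%. The arithmetic is right; the question is the SD.

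**What the pilot figures imply.**
- SD of the paired difference = 81/3.97 × √24 = 99.95 min.
- Total single-night SD = 99.95/√(2 × 0.878) = 75.43 min.
- Between-person SD = √0.122 × 75.43 = 26.35 min, which matches the stated 26.3.
- Within-person SD = √0.878 × 75.43 = 70.68 min.

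So 26.3 min is the random-intercept SD, 12% of single-night variance. Rounding of 1.35 h and 3.97 moves the within-person SD only between 70.3 and 71.0 min.

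**Error SD with k nights averaged per period, nights independent.**
- Change contrast: SD = 70.68 × √(2/k).
- Single time point: SD = √(26.35² + 70.68²/k).

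| Nights k | Change SD (min) | Power, 39 per group | Power, 47 per group | n per group for 80% | Single-time SD (min) | Power, 39 per group |
|---|---|---|---|---|---|---|
| 1 | 99.95 | 16% | 18% | 550 | 75.43 | 22% |
| 4 | 49.98 | 37% | 42% | 138 | 44.08 | 44% |
| 5 | 44.70 | 43% | 49% | 111 | 41.15 | 48% |
| 7 | 37.78 | 54% | 60% | 80 | 37.52 | 54% |

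The 47 per group is 195 × 0.73/3 = 47.45, rounded down. A simulation of the three-arm, three-period random-intercept model at 39 per group gave 16.7%, 37.4%, 42.7% and 53.5% for the change contrast.

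**Difference detectable with 80% power (change contrast).** At 39 per group: 28.4, 25.4 and 21.5 min with four, five and seven nights. At 47 per group: 25.8, 23.1 and 19.5 min.

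**Sensitivity, seven nights.**
- For the change SD to fall to 26.3 min, 2 × (70.68/26.3)² = 14.4 nights per period would be needed, about twice the maximum worn.
- An assumed extra person-by-period SD of 10 or 20 min gives a change SD of √(2 × (70.68²/7 + g²)) = 40.3 or 47.2 min, and power at 39 per group of 49% or 40%.
- If the 10% of actigraphs that D6s expects not to be returned come on top of attrition (an assumption), 195 × 0.73 × 0.9/3 = 42.7 per group, with 56–57% power.
- Adjusting for the baseline weekly mean: r = 26.35²/37.52² = 0.493; SD = 37.52 × √(1 − 0.493²) = 32.64 min; power 64% at 39 and 71% at 47 per group.
- An SD of 26.40 min gives 80% at 39 per group, so the within-person SD would have to be at most 26.40/√(2/7) = 49.4 min.

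**The case against.** The strongest objection is that 70.7 min is a poor guide to ordinary night-to-night variation at home. The pilots flew in before the first night and lengthened their sleep on the second because the workload was high. The SD of that difference therefore mixes nightly noise with differences between pilots in how far they extended sleep. The result is sensitive to this: with seven nights, a within-person SD of 50 min gives 79% at 39 per group and 85% at 47, and 55 min gives 72% and 79%. This stands as a limit on what can be said about true power. It does not support the stated 80%, because the plan chose this source and used only one of its two variance components.

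A second objection is that 54% applies to an unadjusted comparison of one active arm with control at 39 per group. Pooling both active arms (94 against 47) gives 71% with seven nights, and adding baseline adjustment gives 82%. The plan specifies neither step, and it sets 39 for each of the two treatment groups, which points to separate comparisons.

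Third, 26.3 min is the limit of the single-time-point SD as nights accumulate. That is so, but at seven nights the SD is still 37.5 min. The one-, four- and five-night rows are illustrations, since the plan sets no minimum number of valid nights.

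Finally, the calculation concerns one of two primary sleep outcomes, and the timeline in D2 ends data acquisition in April 2019, before the current version of June 2020. The correction therefore bears on how results are read, not on recruitment.

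**Conclusion.** The concern holds. The figure of 39 per group follows from d = 0.57, but d = 0.57 rests on an SD that is not the error SD of either form of the planned test. For the stated 15-min effect, with four to seven usable nights, the pilot data imply that the change contrast would miss a true benefit about 46–63% of the time at 39 per group and 40–58% at 47.

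This assumes that the pilots' night-to-night variance carries over to Veterans, that nights within a person are independent, and that each active arm is compared separately with control without baseline adjustment. Extra person-by-period variation would lower power; a smaller within-person SD, pooled arms or baseline adjustment would raise it. The point is worth correcting because the target of 117 is justified by this figure, but it is confined to the sub-study.

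**What to change.** In D6z, replace the 80% statement with power, or the detectable difference, based on the SD of change in weekly mean sleep duration. Show it as a range by number of usable nights and at the actual number of participants with actigraphy at both periods. State that the pilot variances come from airline pilots. The night-to-night SD in Veterans can be estimated from the pre-treatment actigraphy week, pooled over arms, so no unblinded comparison is needed.

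D6z and the sub-study part of D6x should also describe the same contrast: change from pre-treatment, or difference between arms at each time point.

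Optionally, keep the repeated-measures model and adjust the post-treatment and 3-month contrasts for the baseline weekly mean, labelled as a change to the plan.

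The cost is revised wording and a less favourable stated power. No participants or procedures are added.
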